5.5. Packaging

Nature and Contents of the Container

Victoria Apotheke Zurich will supply blinded product and placebo, package for refrigerated shipping, and manage customs and importation documents.

5.6. Receipt, Storage and Handling of Study Drug

Local site Research Pharmacy will be responsible for receipt, inventory, storage, and destruction of Study Drug.

0008_Protocol v2.5, 08-03-18, AMD.docx

Receipt of Drug Supplies

Any damaged or unusable study drug in a given shipment will be documented by the receiving Pharmacy. The Research Pharmacist will notify the IND Sponsor of any damaged study drug.

Special instructions upon receipt

Open package, review and compare to shipping documents, log inventory counts and refrigerate.

Storage

Nasal spray: Store in a refrigerator (2–8°C or 35.6°F–46.4F). Shelf life: After opening the bottle, store the nasal spray at room temperature (15–25°C) and use within 1 month.

Dispensing of Study Drug

Designated staff from the site Research Pharmacy maintains the Drug Accountability Logs to track how, when and to whom the investigational drug was prescribed, dispensed and assigned to subjects. Study clinical staff will keep drug administration records regarding drug that is damaged or wasted.

Routine study drug administration and reconciliation will be performed based on clinical site policy and standard operating procedures.

Return or Destruction of Study Drug

The procedures for final reconciliation of the site's drug supply at the end of the study will be in accordance with local site Pharmacy standard operating procedures. There are no special precautions cited for disposal of Intranasal Oxytocin.

6. Study Procedures

Study visits. All studies will be performed in the Clinical Research Center at the designated site(s).

6.1. Visit 1 (Consent, Screening for Eligibility, and Baseline Testing – Day 0)

Subjects present in fasting state to the site CRC at appointed time for informed consent processing, medical history and physical exam to assess inclusion and exclusion criteria, including measurements of weight, gait speed, waist circumference, hematology, coagulation studies, chemistry with liver function, lipid panel, urinalysis, and serum and urine osmolality. A 2-hour OGTT will be performed to assess glucose tolerance. Screening mental status assessments (Mini-Cog and depression scale) will be performed to ensure valid consenting process. If subjects meet initial eligibility criteria based on walking speed and history & physical examination. Individuals meeting eligibility will proceed to a 2-hour OGTT. During the 2-hour OGTT, baseline testing will be performed, including labs, food recall and appetite assessments and psychometrics. After the 2-hour OGTT, the participant will be given a meal or substantial snack (per local clinical research unit) and continue with the functional testing. A screening window of 30 days is allowed so that all laboratory and test results can be returned and reviewed. Estimated length of this visit is 6 hours.

- Vital signs will be assessed for blood pressure, heart rate, respiratory rate and temperature
- Walking speed will be assessed at usual speed over a 15-foot course
- Waist circumference will be measured in inches and converted to centimeters.
- Weight in pounds will be measured or calculated in kilograms and used in BMI calculation.
- History & physical examination, targeted to the inclusion & exclusion criteria will be performed to determine study eligibility.

- Laboratory tests: CBC, CMP with liver function, Hemoglobin A1c, coagulation test (PT/INR, PTT), urinalysis, serum osmolality, urine osmolality, lipid panel. Order additional labs, if necessary, based on pertinent medical history.
- Psychometrics: Mini-Cog scoring < 3 will not be studied; Geriatric Depression Scale (GDS) scoring > 7 will not be studied and warrants follow up assessment with mental health professional
- Electrocardiogram (ECG): ECG with definitive evidence of prior myocardial infarction will not be studied
- 2-hour OGTT: Baseline (fasting) samples for determination of glucose and insulin concentrations will be drawn at -30, and -15 minutes (these basal values are averaged). At time zero, each subject will ingest 75 g of glucose. Glucose and insulin are determined every 30 minutes for 2 hours following glucose ingestion. The Matsuda index of insulin sensitivity will be calculated from the OGTT results, as described ¹³.
- Food recall and appetite assessments: A 24-hour food recall, 3-day food diary, and appetite will be assessed using standardized questionnaires^{14, 15}.
- Psychometrics: The Montreal Cognitive Assessment (MOCA) and The Centers for Epidemiologic Studies Depression Scale (CES-D) will be administered for baseline measurement.
- Functional Testing: Timed Up and Go (TUG) and Short Performance Physical Performance Battery (SPPB, modified) will be measured using standardized methods ^{23, 24}. Grip strength will be assessed using handheld digital dynamometer.

6.2. Visit 2: Optional MRI (within 7 days after V1)

MRI (optional): Image of the abdomen and dominant lower extremity will be done if funding is available to examine the effect of oxytocin on abdominal visceral fat and thigh muscle volume as described ²⁵. If participant has a pacemaker or any other reason that would preclude obtaining an MRI, this procedure can be omitted at the discretion of the PI.

6.3. Visit 3 – Physiological measures and Randomization (within 7-14 days after V2)

Subjects present to the site CRC in fasting state to assess body composition, bioimpedance, calorimetry, muscle biopsy, and systemic inflammation. An intravenous (IV) line is placed for access during muscle biopsy.

- Vitals signs, weight and BMI
- DEXA: Whole body dual-energy X-ray absorptiometry is performed to measure lean and fat body mass
- Bioimpedance: Measures weight, body fat percentage, and body mass index (BMI). The BF-350 is an FDA-cleared body composition monitor is an affordable solution for mainstream healthcare and fitness providers. Bioimpedance will be performed at UTMB Galveston site only.
- Calorimetry: Indirect calorimetry is performed in fasting state at rest for 30 minutes. Calorimetry will not be performed at UT Houston due to unavailability of required equipment. Since this is not a major outcome of the study, this does not significantly affect the scientific integrity of the study.
- Muscle Biopsy: Vastus lateralis muscle needle biopsy will be performed to assess muscle fiber type, satellite cells, and inflammatory markers.
- Laboratory and blood draw: Systemic inflammatory markers (see Analyses)

• Adverse event review questionnaire will be completed.

Analyses.

Muscle:

A biopsy of the vastus lateralis muscle will be performed as described using aseptic technique ¹⁷. The following measurements will be performed:

- Muscle fiber cross sectional area (CSA) ¹⁸
- Satellite (stem) cell number and proliferative capacity ^{19, 20}
- Inflammatory genes / proteins. Measurements of NF_KB and MAPK signaling, two key mediators of the inflammation state, will be conducted as described ²¹. We will also assess cellular inflammation by measuring the levels of the mRNA transcripts for IL-1β, IL-6, MCP-1, and TNFα mRNA in skeletal muscle before and after oxytocin treatment²¹.

Blood/plasma:

• Systemic inflammation - measuring plasma concentration of TNF-α, C-reactive protein, IL-6, and adiponectin, using commercially available ELISA kits.

Randomization. Subject will be randomized to study drug or placebo and dispensing occurs at the end of V3.

6.4. Visit 4. Safety Labs (+1 week since start of study drug, within ±3-day window) and drug tolerability Subjects present in facting state to the site CPC to assess:

- Subjects present in fasting state to the site CRC to assess:
 - Vital signs, weight, BMI, waist circumference
 - Safety labs: Chemistry (including serum sodium), liver function, urine osmolality and serum osmolality
 - Food recall: repeat 24-hour food recall, 3-day food diary and appetite assessments (same as Visit 1)
 - Drug tolerability: subjects will be assessed for drug tolerability, including any side effects or adverse effects. Special attention will be made for signs and symptoms suggestive of hyponatremia including lethargy, muscle spasms, seizures, confusion/delirium, nausea and vomiting

6.5. Visit 5 Safety Labs (+4 weeks of drug administration, within ±7-day window) and drug tolerability

Subjects present in fasting state to the site CRC to assess:

- Vital signs, weight, BMI, waist circumference
- Drug compliance and tolerability, AE review
- Psychometrics: repeat MOCA and CES-D
- Food recall: same as Visit 1
- Safety labs: chemistry with liver function, urine osmolality and serum osmolality

6.6. Visit 6; Post treatment measurements (6-7.5 weeks on treatment)

Subjects present in fasting state to the site CRC to assess:

- Vital signs, weight, BMI, waist circumference
- Laboratory: CBC, chemistry with liver function, lipid panel, urine and serum osmolality, hemoglobin A1c, coagulation tests (PT/INR, PTT)
- Functional testing: Gait speed, grip strength, modified SPPB, TUG
- Food recall: same as Visit 1

- 2-hour OGTT
- Drug compliance and tolerability, AE review

6.7. Visit 7: Optional MRI (if done at V2) – (7-7.5 weeks on treatment)

MRI (optional): Image of the abdomen and dominant lower extremity will be done if completed at Visit 2. If participant has a pacemaker or any other reason that would preclude obtaining an MRI, this procedure can be omitted at the discretion of the PI.

6.8. Visit 8: Post treatment measurements (7.5-8 weeks of treatment)

Subjects present in fasting state to the site CRC to assess:

- Vitals signs, weight, BMI, waist circumference
- MOCA, CES-D
- DEXA body composition, Bioimpedance (UTMB Galveston only) and Calorimetry
- Muscle biopsy (satellite cell, fiber type, fat infiltration, inflammation, gene expression)
- Blood draw: Systemic inflammation
- Drug tolerability, compliance, and AE review

See Summary of Visits Table on next page.

Summary of Visits Table

	Visit 1	Visit 2	Visit 3	Visit 4	Visit 5	Visit 6	Visit 7	Visit 8
			240		4 weeks	6-7.5	MRI	7.5-8
	Screen	MDI	V2	1 week on	on	weeks on	7-7.5	weeks on
	(fasting)	+ 7d	(fasting)	(fasting)	(fasting)	(fasting)	treatment	(fasting)
Medical history and	(raoting)		(idotilig)	(luoting)	(luoting)	(luoting)		(luoting)
physical examination.	Х							
ECG								
Vital signs, Weight, BMI	Х		Х	Х	Х	Х		Х
Waist circumference	Х			Х	Х	Х		Х
Mini-Cog	Х							
Montreal Cognitive	v				V			V
Assessment (MOCA)	~				~			~
Geriatric depression scale	V							
(GDS)	X							
Centers for Epidemiologic								
Studies Depression Scale	Х				X			Х
(CES-D)								
Gait speed, 15-foot course	Х					Х		
Electrocardiogram	Х							
**CBC. HobA1c. and								
Coagulation testing	Х					Х		
(PT/INR, PTT)								
**Chemistry with liver								
function, serum osmolality								
(other safety labs if	Х			Х	X	X		
clinically indicated by								
history)								
**Lipid Panel	Х					X		
Urinalysis	Х							
Urine osmolality	Х			Х	Х	Х		
OGTT, 2-hour	Х					Х		
Body composition (DEXA)			Х					Х
Bioimpedance (UTMB								×
only)			Х					^
Calorimetry			Х					Х
Randomization*			Х					
Body composition (MRI)		v					v	
- optional		^					^	
Functional tests: mSPPB,	v					v		
TUG, grip strength	^					^		
24-hour food recall, 3-day	v			v	×	×		
food diary, appetite	^			^	^	^		
Muscle biopsy			Х					X
Systemic inflammation			Х					Х
			AE					
			review	X	X	X		X
compliance, AE review			only					

* After Visit 4, participants may receive periodic phone calls by study staff between study visits to assess any symptoms and encourage adherence to study drug.

** Any marginally abnormal lab findings may be repeated if clinically indicated to ensure initial or continued eligibility.

7. Statistical Plan

7.1. Sample Size Determination

Our power and sample size estimation is based on findings from an 8-week study of intranasal oxytocin in 24 adults, which found a greater reduction in body weight and BMI with oxytocin. Based on their findings, our proposed study (12 completers each site for 36 completers total, 18 completers in each arm) is expected to have 96.4% power to detect the oxytocin effect if the standard deviation (SD) associated with weight loss is 6.0 kg in the oxytocin group and 1.5 kg in the control group. For a more conservative estimate assuming a SD of 6.0 in both the oxytocin and control groups, our study would have 78.2% power. For both these power analyses, we assume type 1 error of P=0.05.

7.2. Statistical Methods

Analytical Approach.

Generalized linear mixed effects model will be used to evaluate the effect of oxytocin on the change of each continuous measure. The effect of oxytocin will be assessed by whether the time by oxytocin interaction is significantly different from 0 with a 2-sided p-value<0.05. Normal transformed score of an outcome will be used in the analyses when appropriate.

8. Safety and Adverse Events

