	8.3	RECORDING AND REPORTING OF SAE/UPIRSO	15
	8.4	MEDICAL MONITORING	16
	8.5	UNBLINDING	17
	8.6	STOPPING RULES	17
9	DATA	A HANDLING AND RECORD KEEPING	18
	9.1	Confidentiality	18
	9.2	Source Documents	18
	9.3	DATA MANAGEMENT	18
	9.4	RECORDS RETENTION	18
10	STUE	DY MONITORING, AUDITING, AND INSPECTING	19
	10.1	STUDY MONITORING PLAN	19
	10.2	AUDITING AND INSPECTING	19
11	ETHI	CAL CONSIDERATIONS	20
12	STUE	DY FINANCES	20
	12.1	FUNDING SOURCE	20
	12.2	CONFLICT OF INTEREST	20
	12.3	SUBJECT STIPEND OR PAYMENTS	20
13	REFE	RENCES	21
14	ATTA	CHMENTS	22
	Α.	PLACEHOLDER FOR SAMPLE CONSENT FORM	23
	В.	PLACEHOLDER FOR EVENT SCHEDULE	24
	C.	PLACEHOLDER FOR DRUG SUPPLIER (VICTORIA APOTHEKE ZURICH/NOVARTIS).	25
	D.	PLACEHOLDER FOR QUESTIONNAIRES AND INSTRUMENTS	26
	Ε.	PLACEHOLDER FOR SUMMARY OF PROTOCOL REVISIONS	27-29

List of Abbreviations

OGTT – Oral Glucose Tolerance Test SPPB – Short Physical Performance Battery SIADH – Syndrome of Inappropriate Antidiuretic Hormone Secretion TUG – Timed Up and Go Mini-Cog – Mini-Cog test - Screening for Cognitive Impairment in Older Adults MoCA – Montreal Cognitive Assessment GDS – Geriatric Depression Scale CES-D – Centers for Epidemiologic Studies Depression Scale

Study Summary

Title	The Physiologic Effects of Intranasal Oxytocin on Sarcopenic Obesity
Protocol Number	OXY-SAR-001
Phase	II
Methodology	Eligible subjects self-administer 24 IU intranasal oxytocin q.i.d. for 8 weeks. The study will examine whether the intervention will promote weight loss and preserve muscle mass, thereby preserving and/or improving physical function in older subjects with sarcopenic obesity.
Study Duration	12 weeks ± 1 week
Study Center(s)	UTHSCSA, UTHealth (Houston), UTMB (Galveston)
Objective	 To assess the effect of intranasal oxytocin administration on body weight, adiposity, muscle mass, and glucose tolerance in older adults. To assess the effect of intranasal oxytocin on physical function and physiologic parameters of insulin signaling, inflammation, and muscle regeneration in older adults.
Number of Subjects	36 completers (3 sites, up to 15 at each site, allowing for attrition)
Inclusion Criteria	Age ≥60 years BMI 30.0-43.0 kg/m ² Sedentary (≤2 strenuous exercise/week) Gait speed < 1 meter/second

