3.3. Study Endpoints

Primary outcomes: Change in weight, adiposity,

muscle mass, and physical function (gait speed, strength, SPPB). This is a pilot study which will examine change in these outcomes prior to and after treatment.

Secondary outcomes: Change in glucose tolerance as measured by OGTT, measures of systemic inflammation (TNF- α , C-reactive protein, IL-6, adiponectin), muscle inflammation (IL-1 β , IL-6, MCP-1, TNF- α mRNA), and muscle stem cell number and proliferative capacity. This is a pilot study which will examine change in these outcomes prior to and after treatment.

Table 2. Outcome variables						
Primary Outcome	Secondary Outcome					
Adiposity (BMI, DEXA)	Glucose tolerance (OGTT)					
Muscle mass (DEXA, MRI, muscle fiber CSA)	Systemic and muscle inflammation					
Physical function (gait speed, muscle strength, balance)	Muscle stem cell number and proliferative capacity					

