4.4. Early Withdrawal of Subjects

4.4.1. When and How to Withdraw Subjects

Subjects have the right to withdraw fully or partially from the study at any time and for any reason without prejudice to his or her future medical care by the physician or at the institution.

Withdrawal of full consent for a study means that the subject does not wish to receive further investigational treatment and does not wish to or is unable to continue further study participation including any follow-up in person, by phone, through third parties including relatives or friends, via discussion with other treating physicians, and by use of medical records; subject data up to withdrawal of full consent will be included in the analysis of the study. Any subject may withdraw full consent to participate in the study at any time during the study. The Investigator or sub-investigator will discuss with the subject appropriate procedures for withdrawal from the study.

Final Study Visit for Withdrawn Subjects

At the time of receiving notification of intended withdrawal, researchers will ask subject to complete a final visit. The informed consent document advises subjects to discuss withdrawal decision with the principal investigator. This visit includes a repeat history and physical examination, weight, functional testing, Bioimpedance (UTMB site only), DEXA, questionnaires, and laboratory tests (safety labs, inflammatory markers). Subjects may choose to complete all or part of the final study visit.

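### Section 7.2 tests every continuous outcome by a time-by-oxytocin interaction without baseline adjustment, giving up modest precision, and leaves the weight and BMI contrast unnamed

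*Combined protocol and SAP*

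**What the plan says.** Section 7.2 has three sentences. The model is given as "Generalized linear mixed effects model will be used to evaluate the effect of oxytocin on the change of each continuous measure". The test is given as "The effect of oxytocin will be assessed by whether the time by oxytocin interaction is significantly different from 0 with a 2-sided p-value<0.05". The third sentence allows a normal-score transformation when appropriate. The synopsis repeats the first two. Neither place names a baseline covariate, a baseline visit, a contrast, a coding of time or a within-subject covariance.

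Section 3.3 describes the comparison only in outline: "This is a pilot study which will examine change in these outcomes prior to and after treatment".

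The visit sections and the Summary of Visits Table give these measurement times:

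- DEXA, muscle biopsy and systemic inflammation: Visits 3 and 8.
- OGTT and function: Visits 1 and 6. Section 6.6 lists "Gait speed, grip strength, modified SPPB, TUG".
- Optional MRI: Visits 2 and 7.
- Weight and BMI: Visits 1, 3, 4, 5, 6 and 8. Section 6.8 begins "Vitals signs, weight, BMI, waist".

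Section 7.1 plans 18 completers per arm. It claims 96.4% power with SDs of weight loss of "6.0 kg in the oxytocin group and 1.5 kg in the control group", and 78.2% with 6.0 kg in both arms.

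**The concern.** The interaction does use baseline, since for a two-visit outcome it equals the between-arm difference in mean change. Subtracting baseline in full is efficient only when pre and post values are almost perfectly correlated. At moderate correlation it carries baseline noise into the comparison, and regressing on baseline removes that noise. With 18 per arm there is little precision to spare, and the baseline values are already being collected.

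Weight and BMI raise a second question. With six visits, a time-by-oxytocin interaction has 5 degrees of freedom if time is categorical and 1 if it is linear. It could also be read as one change between two chosen visits. These tests differ in power. Some also depend on the covariance assumed for repeated weights, so a choice made after seeing the data could affect the result.

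**Working it through.** **1. The plan's own powers.** Section 7.1 does not state the mean difference, so I solved for it. The SD is sqrt((6.0² + 1.5²)/2) = 4.373 kg in the first scenario and 6.0 kg in the second. With 18 per arm, a two-sided normal approximation gives d = (1.960 + z_power) × SD × sqrt(2/18):

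- 96.4% power: d = 5.48 kg.
- 78.2% power: d = 5.48 kg.

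A pooled t test with 34 df gives 5.64 kg from both. One difference of about 5.5 to 5.6 kg therefore reproduces both powers, so they fit a single 1-df comparison of weight change with no covariate.

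**2. Outcomes with one pre and one post value.** Assume equal pre and post variance σ² and correlation ρ.

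- Variance of a change score: 2σ²(1 − ρ).
- Residual variance after regression on baseline: σ²(1 − ρ²).
- Ratio: (1 + ρ)/2.
- Average penalty for estimating the slope with n = 18 per arm: 1 + 1/(2n − 4) = 33/32.

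A change-score t test with 80% power on 34 df has non-centrality 2.884. Divide this by the square root of (1 + ρ)/2 × 33/32 and use 33 df:

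| ρ (assumed) | variance ratio with penalty | non-centrality | power |
|---|---|---|---|
| 0.5 | 0.773 | 3.28 | 89% |
| 0.7 | 0.877 | 3.08 | 85% |
| 0.9 | 0.980 | 2.91 | 81% |
| 0.94 | 1.000 | 2.88 | 80% |
| 0.97 | 1.016 | 2.86 | 79% |

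Break-even is at (1 + ρ)/2 = 32/33, or ρ = 0.94.

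**3. Gait speed.** Eligibility requires less than 1 m/s, which truncates the baseline. If truncation leaves a fraction k of the baseline variance, the ratio becomes (1 + ρ)/[(1 + ρ) + (1 − ρ)k], where ρ is the correlation before truncation. With the cut-off assumed within 0.5 SD of the mean, power is about 82–85% at ρ = 0.5, 80–82% at 0.7 and 79–80% at 0.9.

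**4. Weight.** If change is unrelated to baseline weight, only the penalty remains. In the 6.0/6.0 kg scenario the non-centrality is 5.64/(6.0 × sqrt(2/18)) = 2.82, and 2.82 × sqrt(32/33) = 2.78. Power falls from 78.2% to about 77%, a loss of about 1 point.

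**5. What the open contrast can do to power.** Assume a 5.48 kg difference, SD of change 6.0 kg, linear divergence and three covariance patterns. Visit 8 minus Visit 3 then has 75.9% power by t test. The 5-df visit-by-arm test has 45–78%, and a linear slope 70–95%.

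**6. What the open covariance can do to error.** Suppose all six weights were fitted with only a random intercept while individual trajectories diverge linearly after Visit 3. Simulated type I error at nominal 5%, with assumed visit-to-visit noise of 0.5–1.0 kg, is:

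| SD of weight change, both arms | linear time | categorical time, Visit 3 to Visit 8 contrast |
|---|---|---|
| 6 kg | about 34–38% | about 19–21% |
| 1.5 kg | about 6–28% | about 6–16% |

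If only Visits 3 and 8 are used, it is 5%.

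**The case against.** The strongest reply is that nothing proposed is wrong. The interaction is a valid test for two-visit outcomes, 7.2 does not exclude a covariate, the trial calls itself a pilot, and 3.3 already points to a pre/post comparison. Weight, the only outcome powered in 7.1, gains nothing from adjustment, and gait speed gains little. All of that stands. It makes this an improvement rather than a correction of error. It does not remove the point for less reproducible outcomes. Nor does 3.3 say which of Visits 1 and 3 is the pre value for weight, or which of Visits 6 and 8 is the post value.

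Three stronger readings are tempting, and the documents do not support them.

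- A reader might infer from the table in step 6 that the planned analysis has a type I error of 30% or more. No passage proposes a random-intercept-only model, the term mixed effects does not limit the model to one, and the higher figures need an SD of weight change near 6 kg.
- A reader might infer that baseline adjustment rescues the trial from dropout. The synopsis allows for attrition ("36 completers (3 sites, up to 15 at each site, allowing for attrition"), but 7.2 already specifies a mixed model and 4.4.1 states that "subject data up to withdrawal of full consent will be included in the analysis of the study". A completers-only regression is not the plan. For outcomes with a single post value, a baseline-covariate model does not recover withdrawals.
- A reader might infer from the SDs of 6.0 and 1.5 kg that a pooled variance is seriously wrong. At the planned 18 v 18, a pooled test has about 5.6% error.

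**Conclusion.** The point holds as a modest one and should be addressed. The planned test is valid for two-visit outcomes but forgoes about 5 to 9 points of power at correlations of 0.5 to 0.7. The gain shrinks to about 1 point at 0.9 and turns into a loss of about 1 point at 0.97. These figures assume 80% starting power, equal pre and post variance and 18 per arm. Which outcomes fall at which correlation cannot be read from the documents. For weight and BMI the issue is specification: 7.1 powers one 1-df comparison of change, and 7.2 does not commit the analysis to it. Inflated error is a possibility that the wording leaves open, not a property of the stated plan.

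**What to change.** Keep the mixed model and add a few sentences to 7.2.

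- Adjust each outcome for its last pre-drug value: Visit 3 in general, Visit 1 for function and OGTT, Visit 2 for MRI. Do this with a covariate or by constraining baseline means to be equal across arms.
- For weight and BMI, treat visit as categorical, with an unstructured within-subject covariance and Kenward-Roger or Satterthwaite degrees of freedom. Define the effect as the 1-df oxytocin-minus-placebo difference at Visit 8.
- Use an unequal-variance or small-sample robust standard error only as a sensitivity analysis.

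The cost is section wording, one or two degrees of freedom, and about 1 point of power for outcomes with very high pre/post correlation. No visit, measurement or participant is added.
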